Prior approval by the sponsor is expected in those situations in which the Investigator anticipates, contemplates or makes a conscious decision to depart from procedures specified in the protocol. Prior approval is generally not expected in situations where unforeseen circumstances are beyond the Investigator's control, but is still considered a deviation (eg. a trial subject who fails to attend a scheduled follow-up visit, a trial subject too ill to perform a protocol-required test). To obtain approval, the Investigator must call or email and discuss the potential deviation with the Medtronic trial manager or designee prior to initiating any changes. If approval is granted, the Medtronic trial manager or designee will provide the applicable documentation to be maintained in the site files.

FDA regulations require the Investigator to notify the sponsor and the reviewing IRB/MEC within 5 working days of the following deviations [21 CFR 812.150]:

- a deviation from protocol to protect the life or physical wellbeing of a patient in an emergency
- failure to obtain an informed consent

Investigators or an authorized designee must notify Medtronic as soon as possible by calling the trial manager or designee and completing the protocol deviation form.

The Investigator is required to adhere to local IRB/MEC procedures for reporting deviations.

The DSMB may review protocol deviations to ensure compliance and overall trial integrity.

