#### *C.6.6 Missing Data and Planned Sensitivity Analyses (Primary Objective)*

Every effort will be undertaken to minimize missing data. However, some missing data is inevitable, and the trial is designed with the expectation that there may be up to 6% of primary data missing at 24 months. The reasons for missing data will be described in detail and evaluated for assessment of possible bias. The distribution of prognostic factors between patients with data and those without data will be examined to evaluate any potential sources of bias.

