##### C.6.7.2 Analysis of ITT and mITT Populations

For the subjects in the randomized population the primary analysis of the primary endpoint and inferential statistics for the following secondary endpoints will be performed on the ITT and mITT populations:

- Major adverse cardiovascular and cerebrovascular events (MACCE)
- Individual MACCE components
- Major adverse events (MAE)
- Conduction disturbance requiring permanent pacemaker implantation
- NYHA
- Six-minute walk test
- Ratio of days alive out of hospital versus total days alive
- Quality of life
- Echocardiographic assessment of valve performance
- Aortic valve disease-related hospitalizations
- Cardiovascular deaths and valve-related deaths
- Strokes and TIAs
- Per-procedural neurological injury
- Index procedure-related MAEs

- Length of index procedure hospital stay
- Device success
- Procedure success

C.6.7.3 Analysis of Implanted Population

The endpoints listed in C.6.7.2 will also be performed on the implanted population. Additionally, the implanted population will be used for analyzing the primary endpoint, secondary endpoint of prosthetic valve dysfunction, and echocardiographic assessment of valve performance.

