- The incidence of conduction disturbance requiring permanent pacemaker implantation will be provided at 30 days, 6 months, 12 months, 18 months, 24 months, and annually thereafter up to 5 years, separately for new onset and pre-existing conduction disturbance. The statistical method will be the Bayesian version of a comparison of proportions (with predictions).
8. Change in NYHA class from baseline at 30 days, 6 months, 12 months, 18 months, 24 months, and annually thereafter up to 5 years.
- For each subject with paired data, the number of classes changed from baseline (-3, -2, -1, 0, 1, 2, or 3) will be calculated at 30 days, 6 months, 12 months, 18 months, 24 months, and annually thereafter up to 5 years. The endpoint will be evaluated between groups using a Bayesian version of a t-test.
9. Change in distance walked during 6-minute walk test (6MWT) from baseline to 30 days, baseline to 12 months, and baseline to 24 months.

All subjects who are able to perform the six-minute walk evaluation at the time of the follow-up visit will be included in the analysis.

The endpoint will be evaluated using a Bayesian version of a t-test.

10. Ratio of days alive out of hospital versus total days alive assessed at 12 months and 24 months follow-up.

The proportion of post procedure days alive out of hospital against total days alive will be compared between groups at 12 and 24 months. The numerator will be the number of days alive out of hospital, and the denominator will be the number of post procedure days alive as of the last follow-up date. All hospitalizations will be included in this analysis, including hospitalization for device implant.

In addition, days alive out of hospital will be compared between groups at 12 months and 24 months.

The endpoint will be evaluated using a Bayesian version of a t-test.

11. Quality of Life (QoL) change from baseline at 30 days, 3 months, 6 months, 12 months, 18 months, 24 months, and annually thereafter up to 5 years.

The Kansas City Cardiomyopathy Questionnaire (KCCQ), SF-36, and EuroQoL (EQ-5D) will be assessed at baseline, 30 days, 6 months, 12 months, 18 months, 24 months, and annually thereafter up to 5 years. SF-36 and EQ-5D will also be assessed at 3 months. All subjects completing the questionnaires will be evaluated and the reasons for missing data will be provided.

The endpoint will be evaluated using a Bayesian version of a t-test .

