It is not necessary to “pass” all objectives in one subfamily in order to test the objective(s) in the other subfamily. For the purposes of seeking claims, these objectives will only be evaluated once, at the same time as non-inferiority of the primary objective is established. The only exception to this is the primary endpoint superiority test, which carries the possibility of a delayed determination of superiority (as described in Section 4.2.1) and may thus meet its success criterion at a different time.

The remaining secondary objectives may be of interest for scientific or financial reasons but will not be the basis for supporting labeling claims; they are thus outside of the hierarchical testing procedure. Similarly, for those objectives that test non-inferiority, if non-inferiority is established, a test of superiority will also be conducted, but unless specifically itemized in the list, such superiority testing is not part of the hierarchical testing procedure; these superiority tests may be of interest for scientific or financial reasons but will not be the basis for supporting labeling claims.

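### The six-minute walk comparison (secondary endpoint 9) keeps only subjects able to walk at the visit, so it is conditional on a post-randomization outcome and is not the ITT/mITT inference stated in C.6.7.2

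*Combined protocol and SAP*

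**What the plan says.** - C.6.8.1, item 9, defines the endpoint as "Change in distance walked during 6-minute walk test (6MWT) from baseline to 30 days, baseline to 12 months, and baseline to 24 months", compared between arms with a Bayesian version of a t-test. The analysis set is given in one sentence: "All subjects who are able to perform the six-minute walk evaluation at the time of the follow-up visit will be included".
- C.6.7.2 includes the six-minute walk test in the list for which "inferential statistics for the following secondary endpoints will be performed on the ITT and mITT populations".
- C.6.6, the missing-data section, is confined by its title to the primary objective.
- For quality of life (C.6.8.1, item 11) the plan adds: "All subjects completing the questionnaires will be evaluated and the reasons for missing data will be provided". Item 9 has no such commitment.
- C.4.18 foresees the situation, giving "a trial subject too ill to perform a protocol-required test" as an example of a deviation outside the investigator's control.
- The walk test is not among the endpoints listed in C.6.10.1 for labeling claims. C.6.10 says of such remaining objectives that "they are thus outside of the hierarchical testing procedure".

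**The concern.** The rule selects on the outcome after randomization. A subject who walked at baseline and cannot walk at 30 days because of a stroke, heart failure or slow recovery sits at the bottom of the measured scale, yet leaves the analysis. Subjects who have died leave it too.

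A difference in inability between arms is plausible, above all at 30 days. SAVR involves splitting the sternum (C.4.7.2), TAVI uses iliofemoral access by default (C.4.7.1), and the visit window opens at day 30 − 7 = 23 (C.4.9). Treatment is not blinded (C.4.5) and item 9 does not define ability, so site staff who know the assignment decide who enters the comparison.

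At stake is how endpoint 9 is read. A difference among walkers could be taken as the effect of assignment on walking capacity when the two arms contribute differently selected subsets.

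**Working it through.** **1. What the plan supplies.** The plan has no walk-test figure to reproduce: no baseline distance, SD, expected effect or expected proportion unable. Two planning inputs bear on the analysis set: 1600 mITT subjects (C.6.5.2) and an assumed 24-month mortality of about 15% (sample size justification). Deaths alone would then remove 0.15 × 1600 = 240 subjects by 24 months, leaving 1360.

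**2. The two sections side by side.** C.6.7.2 states inference on ITT and mITT, which are defined by randomization and by an attempted procedure (C.6.4.2). Item 9 adds ability to walk at the visit, known only later. A walkers-only set delivers neither population, and no rule shown says how the rest are counted.

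**3. Counting inability as 0 m (inputs assumed).** Let walkers in both arms gain m, unable subjects have baseline distance b, and a proportion p be unable. The arm mean is (1 − p)m − pb. The walkers-only difference is 0. Counting everyone alive, the difference against the arm with more unable subjects is (p₂ − p₁)(m + b).

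| Unable, arm 1 vs arm 2 | m = 30, b = 150 | m = 50, b = 250 |
|---|---|---|
| 5% vs 5% | 0 | 0 |
| 5% vs 10% | 0.05 × 180 = 9 m | 0.05 × 300 = 15 m |
| 5% vs 15% | 0.10 × 180 = 18 m | 0.10 × 300 = 30 m |
| 10% vs 20% | 0.10 × 180 = 18 m | 0.10 × 300 = 30 m |

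**4. Selection on follow-up capacity, without a 0 m score (inputs assumed).** Baseline 260 m (SD 110), change 40 m (SD 80), independent; those with the lowest follow-up capacity are unable. Removing the lowest fraction q raises the mean change among walkers by [80² / √(110² + 80²)] × φ(z_q)/(1 − q). The first factor is 6400/136.0 = 47.05. The second is 0.109 at q = 5%, 0.195 at 10% and 0.274 at 15%.
- 5% vs 10%: 47.05 × (0.195 − 0.109) ≈ 4 m in favour of the arm with more unable subjects.
- 5% vs 15%: 47.05 × (0.274 − 0.109) ≈ 8 m.

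In simulation a true deficit of 20 m in that arm appeared as 15.9 m and 12.0 m respectively.

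**5. Selection on baseline distance only (inputs assumed).** Same baseline, 5% vs 15% unable, no true difference, and weaker subjects improving more. The walkers' mean baselines differ by 110 × (0.274 − 0.109) ≈ 18 m. With a slope of change on baseline of −0.2 the shift is about 4 m, and with −0.4 about 7 m, now against the arm with more unable subjects. With slope 0 there is no shift.

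**The case against.** The strongest reply concerns consequence. The endpoint supports no labeling claim, and disability and death are counted elsewhere: in the primary endpoint, the Clinical Efficacy composite, the separate stroke analysis, NYHA change, KCCQ and days alive out of hospital. That stands, and it limits the weight of the point. Those analyses do not correct this comparison, however, and none listed counts who could not walk.

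Second, a reader might infer that the arm with more disabled patients will look better outright, or that mean change is overstated in both arms whatever the mechanism. The documents support neither. Suppose, purely for illustration, a baseline of 250 m, walkers changing by −10 m on SAVR and +15 m on TAVI, and 20% versus 8% unable. SAVR still looks worse by 25 m among walkers. With 0 m scoring the means are 0.80 × (−10) + 0.20 × (−250) = −58 m and 0.92 × 15 + 0.08 × (−250) = −6.2 m, a gap of 51.8 m. The walkers-only gap is narrower, not reversed. Step 5 shows that even the direction depends on why subjects cannot walk.

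Third, scoring inability as 0 m is a convention, and it produces most of the larger figures. As a main analysis it would make an unblinded judgement of medical inability worth the subject's whole baseline distance. Applied at baseline as well, it would create very large apparent gains in a t-test on means. It would also leave deaths out. This stands, and is why 0 m scoring belongs among the sensitivity analyses.

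Finally, the separate SAP and the text of Appendix R.14 (walk-test instructions) were not in the material reviewed and may contain a rule for tests not done. Item 9 would still have to agree with it.

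**Conclusion.** The point holds in limited form. Item 9 states a rule that conditions a between-arm comparison on a post-randomization outcome, and in the text reviewed nothing offsets it. It does not deliver the inference stated in C.6.7.2. The arm with more unable subjects looks better than it should if inability differs by arm and reflects poor follow-up status. Unequal removal causes no such shift when the proportions and the mechanism are the same in both arms, and the shift can reverse when inability is driven only by low baseline distance.

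The size cannot be computed from the documents. The ranges of 4 to 8 m and 9 to 30 m rest on assumed distances, changes and proportions unable, and the second also on the 0 m convention. A reader might infer a threat to the primary result or to a labeling claim; the primary endpoint uses other data and the walk test is not in the claim list, so neither follows.

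**What to change.** 1. Keep the walkers-only result in C.6.8.1, item 9, but label it as conditional on being able to walk at the visit.
2. Add a reason-not-done code to the walk-test form, with a written definition of medical inability because sites are unblinded. Report by arm and visit the numbers dead, unable for a medical reason, and missing for other reasons. Deviation forms under C.4.18 already capture part of this.
3. Pre-specify a companion between-arm analysis of all mITT subjects that is rank-based, with death worst, medical inability next and walkers ordered above them. State how tests missed for other reasons and subjects with no baseline distance are handled.
4. Add 0 m scoring of inability among survivors as a further sensitivity analysis.
5. Reconcile item 9 with C.6.7.2, and align the SAP and Appendix R.14 if they carry a rule.

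No new visit or test is needed. The cost is a form field, a little more analysis work, and a companion result that is not expressed in metres.

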#### C.6.5.2 Randomization, Sample Size and Analysis Plan

Randomization will follow a 1:1 (treatment:control) allocation ratio and be stratified by site and need for revascularization, using a blocked randomization scheme with blocks of randomly varying sizes. The sample size for the mITT population is 1600 subjects.

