12. Echocardiographic assessment of prosthetic valve performance at discharge, 6 months, 12 months, 24 months, and annually thereafter up to 5 years using the following measures:

- transvalvular mean gradient
- effective orifice area
- degree of prosthetic aortic valve regurgitation (including transvalvular and paravalvular)

The four echocardiographic measurements will be evaluated at discharge, 6 months, 12 months, 24 months, and annually thereafter up to 5 years. All implanted subjects undergoing echocardiography procedures will be evaluated.

Continuous measures will be evaluated using a Bayesian version of a two-sample t-test. Categorical variables will be evaluated using Bayesian version of a comparison of polytomous outcomes.

Additionally, incidence of moderate/severe aortic insufficiency at discharge will be compared between groups using the Bayesian version of a comparison of proportions.

13. Aortic valve disease related hospitalizations

The number of subjects re-hospitalized after the initial index procedure will be compared at 30 days, 6 months, 12 months, 18 months, 24 months, and annually thereafter up to 5 years.

Incidence of recurrent hospitalization will be provided at 30 days, 6 months, 12 months, 18 months, 24 months, and annually thereafter up to 5 years. The statistical method will be the Bayesian version of a comparison of proportions (with predictions).

14. Cardiovascular deaths and valve-related deaths

The number of subjects experiencing cardiovascular deaths and valve-related deaths at 30 days, 6 months, 12 months, 18 months, 24 months, and annually thereafter up to 5 years. Incidences will be compared between groups. The statistical method will be the Bayesian version of a comparison of proportions (with predictions).

15. Strokes and TIAs

The number of subjects with strokes (of any severity) and TIAs at 30 days, 6 months, 12 months, 18 months, 24 months, and annually thereafter up to 5 years. A separate analysis will be performed for each of the following:

- a composite of all strokes and TIAs
- disabling strokes only
- non-disabling strokes only
- TIAs only

The statistical method will be the Bayesian version of a comparison of proportions (with predictions).

Additionally, incidence of all strokes at 30 days or hospital discharge, whichever is longer, will be compared between groups using the Bayesian version of a comparison of proportions.

16. Peri-procedural Neurological Injury (Stroke, TIA, Encephalopathy)

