### C.6.10 Multiplicity Considerations

It is recognized that with a multiplicity of tests comes inflation in the chance of a false finding of superiority or non-inferiority. Therefore, for the purpose of seeking approved labeling claims on designated secondary objectives, the following standard will be used: If the primary objective demonstrates non-inferiority, claims will be sought for selected secondary non-inferiority and superiority objectives and for superiority on the primary objective metric. These will be tested via a hierarchical (sequential) order that preserves the overall study-wise type I error rate at the level of 0.05, while requiring all non-inferiority tests to meet a nominal type I error rate of 0.05 and all superiority tests to meet a nominal type I error rate of 0.025. The testing order is specified below. The following objectives are tested in order, and testing continues if and only if all previous objectives have met their designated success criterion.

1. Primary endpoint (non-inferiority)
2. Transvalvular mean gradient at 12 months (non-inferiority)
3. Effective orifice area at 12 months (non-inferiority)
4. Change in NYHA classification from baseline to 12 months (non-inferiority)
5. Change in KCCQ score from baseline to 30 days (non-inferiority)

All of the above are non-inferiority tests and are tested with a type I error standard of 0.05. If all of the above tests meet their success criterion, the type I error rate of 0.05 that is passed on from the above tests will be split equally (using a Bonferroni justification) between the following parallel subfamilies, so that each subfamily is tested using a type I error rate of 0.025:

Subfamily #1: Primary endpoint (superiority)

Subfamily #2: Secondary (superiority) objectives #5–#18 as enumerated below, tested in ordered sequence such that all  $\alpha$  is passed on to subsequent tests if a test criterion is met, while all testing stops if a test criterion is not met. This procedure controls the type I error rate of this subfamily at the level 0.025.

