where  $\pi_{TAVI}$  and  $\pi_{SAVR}$  denote the proportion of subjects with moderate/severe aortic insufficiency at the discharge echo. The posterior probability  $P(H | \text{data})$  will be calculated and compared to a threshold of 0.975. The statistical method will be the Bayesian version of a comparison of proportions (see Section C.11).

18. New pacemaker implant rate for TAVI at 30 days or hospital discharge, whichever is longer (secondary objective #7). The hypothesis of interest is

$$H: \pi_{TAVI} < 30\%$$

where  $\pi_{TAVI}$  denote the binary rate of new pacemaker implants for TAVI at 30 days or hospital discharge (if longer). The posterior probability  $P(H | \text{data})$  will be calculated and compared to a threshold of 0.975. The statistical method will be the Bayesian version of a comparison of proportions (see Section C.11).

Other than the hierarchical testing procedure described above, no further multiplicity adjustments will be made in the analyses of the secondary endpoints. Summary data from other secondary objectives, such as device success and procedural success from secondary objectives #20 and #21, respectively, may be provided in the device labeling. However, no claims of statistical significance or other statistical inference will be made.

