**Note: Velocity tracings should be noted on images submitted for Screening Committee review**

**Note: Fine linear signals at peak velocity should not be included in the velocity tracings!**

## 12. Assessment of Aortic Regurgitation

- **Use all echo modalities:** An integrated exam approach using colour flow, pulsed-wave (PW), and continuous-wave (CW) Doppler is used to assess the severity of transvalvular and paravalvular regurgitation.
- **Use four views:** Colour flow Doppler imaging should be performed from the parasternal long and short-axis views, and the apical long-axis and apical 5-chamber views. A recording of the aortic regurgitant signal should be obtained with CW Doppler. If the degree of aortic regurgitation appears more than mild by visual estimate, the velocity in the proximal descending aorta and the abdominal aorta should be recorded with PW Doppler.
- **Severity:** The degree of transvalvular and paravalvular AR will be graded as none, trace, mild, moderate, and severe based on the analysis of the parameters shown in Table 2a.
  - The category of “trace” is used in cases where regurgitation is barely detectable by colour Doppler.
  - Regurgitant signals observed to originate within the stent will be considered transvalvular, and regurgitant signals observed to originate outside the stent will be considered paravalvular.
- Paravalvular regurgitant jets will be characterized by the extent of the aortic regurgitant jet relative to the short axis circumference of the aortic valve (Table 2a- Valve Academic Research Consortium (VARC) Consensus Report for Transcatheter Aortic Valve Implantation (TAVI) and Table 2b. Updated standardized endpoint definitions for transcatheter aortic valve implantation: the VARC-2 consensus document, and Table 3a and b -2008 Focused Update Incorporated Into the ACC/AHA 2006 Guidelines for the Management of Patients With Valvular Heart Disease (published in the October 2008 issues of Journal of the American College of Cardiology and Circulation).

**Table 2a.** Parameters for evaluation of the severity of aortic regurgitation

Prosthetic Aortic Valve Regurgitation Criteria (Central and Paravalvular)			
Parameter	Mild	Moderate	Severe
Valve Structure and Motion Mechanical or bioprosthesis	Usually normal	Usually abnormal†	Usually abnormal†

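### Prosthetic regurgitation, graded on an ordered scale, is compared as a polytomous outcome with no stated order or direction; naming an ordinal analysis would be a cheap improvement to a supportive endpoint

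*Combined protocol and SAP*

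**What the plan says.** Protocol C.6.8.1, endpoint 12, lists three echo measures: mean gradient, effective orifice area and "degree of prosthetic aortic valve regurgitation (including transvalvular and paravalvular"). They are assessed at discharge, 6, 12 and 24 months, then yearly to 5 years. The first two are continuous, so the sentence "Categorical variables will be evaluated using Bayesian version of a comparison of polytomous outcomes" applies to regurgitation.

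Appendix R.7, section 12, fixes the scale: "The degree of transvalvular and paravalvular AR will be graded as none, trace, mild, moderate, and severe".

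Endpoint 12 then adds a second analysis: "incidence of moderate/severe aortic insufficiency at discharge will be compared between groups using the Bayesian version of a comparison of proportions". In C.6.10.1 this becomes labeling test 17, where the two rates "denote the proportion of subjects with moderate/severe aortic insufficiency at the discharge echo". Its hypothesis is directional (TAVI rate below SAVR rate), with a posterior threshold of 0.975.

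C.6.7.2 lists echocardiographic valve performance among the endpoints given inferential statistics. The full-scale comparison is not in the labeling sequence. C.6.10 says of such objectives: "The remaining secondary objectives may be of interest for scientific or financial reasons but will not be the basis for supporting labeling claims".

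**The concern.** Five ordered grades carry a direction: a subject moves towards better or worse. A comparison of category probabilities that does not use the order spreads the evidence over four contrasts, and a positive answer means only that the two grade distributions differ. The useful statement for a valve trial is whether one arm leaks more, and by how much, at each visit.

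The discharge comparison supplies a direction at one visit and one cut, and it cannot see movement among none, trace and mild. After discharge, no planned between-arm analysis addresses regurgitation alone with a stated direction:

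- Clinical Efficacy (endpoint 5) and Time-Related Safety (endpoint 6) include moderate or severe regurgitation only alongside other events.
- The MAE components (endpoint 3) include prosthetic valve dysfunction, which is wider than regurgitation.
- Endpoint 22 (valve dysfunction) is assessed in TAVI subjects only.

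The plan uses order elsewhere. NYHA class (endpoint 8) is analysed as the number of classes changed. No reason is given for treating regurgitation differently.

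**Working it through.** **Plan's own figure.** None exists for this endpoint: no power, effect size or grade distribution is stated for regurgitation. The powered figure is the single-look total of 1258 for the primary endpoint (C.6.5.2), and it reproduces. With restricted rates 0.2105 and 0.1405, n per arm = (1.645 × √0.2870 + 1.645 × √0.2822)² / 0.07² = 628.6, so 629 per arm and 1258 in total. The trial was sized on mortality and stroke.

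**Inputs from the plan.** Five grades (R.7). "The sample size for the mITT population is 1600 subjects", randomized 1:1, so about 800 per arm. C.6.10 requires "all superiority tests to meet a nominal type I error rate of 0.025", taken here as 0.05 two-sided. This endpoint has no assigned error rate of its own.

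**Assumptions.** Nominal reading of the method. A frequentist analogue, because the Bayesian model is not described in the text available. Illustrative grade distributions. Echo endpoints use implanted subjects with an echo, so 650 per arm is also tried.

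**Step 1, degrees of freedom.** Give an ordinal (1 df) and a nominal (grades − 1 df) chi-square test the same noncentrality λ. Power = P(χ²(df, λ) > 95th percentile of χ²(df)). At λ = 7.85:

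| Test | df | Power | Loss (points) |
|---|---|---|---|
| Ordinal | 1 | 80.0% | – |
| Nominal, 3 grades | 2 | 70.9% | 9.1 |
| Nominal, 4 grades | 3 | 64.5% | 15.5 |
| Nominal, 5 grades | 4 | 59.5% | 20.5 |

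For five grades, ordinal power of 50, 60, 70, 90 and 95% becomes 31, 39, 48, 74 and 84%. The loss is about 19 to 22 points when ordinal power is 50 to 80%, and it shrinks above that.

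**Step 2, common odds ratio.** For each cut k, odds(grade ≤ k) in one arm = odds(grade ≤ k) in the reference arm / OR. Example: reference 50/25/20/4/1% and OR 1.3 give 43.5/26.3/23.8/5.1/1.3%. I simulated 8,000 trials per row at 800 per arm, comparing a tie-corrected Wilcoxon test with a Pearson chi-square. Simulation error is about 0.6 points.

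| Reference grades, none to severe (%) | OR | Ordinal (%) | Nominal (%) | Loss (points) |
|---|---|---|---|---|
| 50/25/20/4/1 | 1.3 | 81.4 | 60.6 | 20.8 |
| | 1.5 | 99.4 | 95.9 | 3.5 |
| | 2 | 100 | 100 | 0 |
| 70/20/8/1.5/0.5 | 1.3 | 72.0 | 49.5 | 22.5 |
| | 1.5 | 97.8 | 90.2 | 7.6 |
| | 2 | 100 | 100 | 0 |
| 40/25/25/8/2 | 1.3 | 82.2 | 62.9 | 19.3 |
| | 1.5 | 99.5 | 96.6 | 2.9 |
| | 2 | 100 | 100 | 0 |

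At 650 per arm with 70/20/8/1.5/0.5%, OR 1.5 gives 94.2% against 81.6%, a loss of 12.6 points.

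**Step 3, what shift this is.** Score the grades 0 to 4. In the first distribution OR 1.3 moves the mean grade from 0.81 to about 0.945, roughly 0.135 of a grade; OR 2 moves it by 0.37. The 20-point loss therefore concerns small shifts.

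**Step 4, non-uniform shift.** With 60/20/15/4/1% against 55/27/13/4/1% at 800 per arm, nominal power is about 78% and ordinal about 25%. Part of the change is towards worse grades and part towards better, and an ordinal test averages them.

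**The case against.** **The method may already be ordinal.** Polytomous means more than two categories; it does not mean unordered. C.6.5.2 defers analysis detail to the SAP, and C.6.10.1 sends its Bayesian methods to a Section C.11 that is not in the text available. A reader might infer that the plan ignores the order. The wording does not establish that; it establishes only that no order is stated. This stands in full.

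**A direction is given.** A reader might also infer that the plan never says which arm has more regurgitation. Labeling test 17 does so for moderate/severe at discharge, and endpoints 3, 5 and 6 carry regurgitation forward within wider outcomes. This stands for discharge. It does not supply a directional analysis of the grade itself, or of regurgitation alone, at later visits.

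**The power figures come from a different method.** The plan is Bayesian, and even a nominal model yields grade probabilities by arm from which a direction could be derived. That is fair: the figures indicate size and are not operating characteristics of the plan. But no such summary is specified.

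**The loss is selective.** A reader might take 20 points as a property of the plan. It depends on five grades, a uniform shift and a small effect. The VARC-2 table in O.2 has only mild, moderate and severe regurgitation, where the loss at 80% ordinal power would be about 9 points. For a shift approaching a whole grade there is no loss, and Step 4 shows the nominal comparison can win. This stands, and it limits the claim.

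**Nothing is decided on this analysis.** Correct: it is unpowered and outside the labeling sequence.

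**Conclusion.** The point holds in limited form. Endpoint 12 assigns an ordered scale to a comparison whose use of order, summary measure and direction are unstated, and this matters most after discharge. If the comparison is nominal, the cost runs from none to about 22 points of power. It is near the top of that range only for small uniform shifts, and 3 to 8 points at an odds ratio of 1.5 with 800 per arm. These sizes rest on assumed grade distributions and a frequentist analogue. The documents do not show that order is discarded, that a fixed amount of power is lost, or that no direction is available at discharge. The consequence is confined to supportive inference: the primary endpoint, the labeling tests and the sample size are untouched.

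**What to change.** In C.6.8.1, endpoint 12, and the matching SAP text:

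- Replace the polytomous comparison of regurgitation grade with a named Bayesian ordinal analysis. Either a cumulative-odds model, or the posterior probability that a randomly chosen TAVI subject has a worse grade than a randomly chosen SAVR subject, would serve.
- State the number of grades used, and report the posterior probability of direction at each echo visit.
- Keep the grade percentages by arm at every visit.

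If the method section already specifies an ordered model, saying so in endpoint 12 and adding the direction summary is enough.

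The cost is wording and analysis code, with no change to data collection, sample size, error rates or labeling test 17. The downside is that one ordinal summary describes a non-proportional shift less well, as Step 4 of the working shows; the grade tables cover that case.
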